Parents will attend a 60-minute orientation at the start of the intervention to review study logistics: telehealth visit setup, prioritizing modules, and setting study expectations. Week 1, dyads will attend a meeting with their health coach to launch the program that will last up to 60 minutes. Dyads will then attend weekly 30-minute sessions with their coach weeks 2-12 (intensive phase) and bi-weekly 30-minute sessions with their coach weeks 13-24 (maintenance phase). During the intensive phase, all dyads will receive the same 12 modules; however, during the maintenance phase, dyads will select the topics of their choice for each session (see Session Outline document). Sessions follow a behavior therapy approach, including guided goal-setting, self-monitoring, identifying barriers and solutions, contingency management, stimulus control, dealing with setbacks, maintenance and relapse prevention. Weight is assessed weekly by coaches, with MI-consistent, autonomy-supportive feedback provided. Weeks 2-4, parents will have one, 60-minute visit with their coach; this will occur again during weeks 12-15. These individual parent sessions will focus on ways to support their child's weight management. Dyads will also be sent weekly exercise videos (1x/week for 30 min) and be encouraged to participate in them. All sessions will be conducted virtually utilizing Zoom or EPIC.

Participants will be provided scales to be used for weekly self-weighing and will be provided guidance on self-regulation by their coach.

ASSESSMENTS:

All assessments will occur at baseline, 3-, and 6-months (primary) unless otherwise noted.

CHILD:

- Trained staff measure height and weight to the nearest 0.1cm and 0.1kg using a precision stadiometer and digital scale, respectively. BMI will be calculated (kg/m²).
- Children will complete the following psychosocial measures via REDCap:
 - The Authoritative Parenting Index (Jackson et al, 1998) will assess child report of parenting style
 - A subset of questions from Project Eat (Neumark-Sztainer, 2002 et al) will be used to assess eating and weight-related habits
 - 2 item physical activity scale (Prochaska et al., 2001) assessing weekly engagement in physical activity.
 - Children's Eating Disorder Examination Questionnaire (Kliem et al, 2017) will assess eating disorders.
- Children will complete the Automated Self-Administered 24-Hour (ASA24®) from NCI that assesses dietary intake.

PARENT:

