- Trained staff measure height and weight to the nearest 0.1cm and 0.1kg using a precision stadiometer and digital scale, respectively. BMI will be calculated (kg/m²).

- Parents will complete the following psychosocial measures via REDCap:
 - Demographics (baseline only) will assess household income, family structure, weight management treatments
 - Food insecurity (USDA, 2012) will be assessed
 - Home Food Inventory (Fulkerson et al, 2008) will assess what food is available in the home
 - The Standardized Screening Tool for Health (Billionix et al, 2017) will assess health-related social needs that negatively impact health
 - Parenting Style Dimension Questionnaire short version, authoritative parenting subscale (Robinson et al, 2001) will assess parent report of parenting style
 - 2 item physical activity scale (Prochaska et al., 2001) assessing weekly engagement in physical activity.
 - A subset of questions from the Family Mealtime Environment (Berge et al 2016) questionnaire will assess the household environment during family meals
 - Modified NHANES sleep time questions (Centers for Disease Control and Prevention (CDC). National Center for Health Statistics (NCHS). National Health and Nutrition Examination Survey Data. Hyattsville, MD: U.S. Department of Health and Human Services, Centers for Disease Control and Prevention) will assess

Attendance and adherence will be monitored. At the 6-month assessment only, all participants will complete an Exit Survey assessing: intervention likes/dislikes; perceived benefits and barriers to implementing intervention goals; overall satisfaction; and suggestions for improvement.

STATISTICAL ANALYSIS:

A proposed sample size of 50 dyads, or parent-child pairs, will allow investigators to establish feasibility and proof of concept. Primary outcomes will be determined with percentage calculations ($[\text{actual}/\text{target}]*100$) to determine percent recruited, percent retained, and percent satisfied. Secondary outcomes will be examined using descriptive statistics to calculate scale means and standard deviations at assessment time points. Paired samples t-tests will be used to examine changes in secondary outcomes over the course of the 6-month intervention.

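### Percent satisfied is a primary outcome, but its only described source is a 6-month Exit Survey, with no described route to families who withdraw or are lost earlier

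*Combined protocol and SAP*

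**What the plan says.** The Statistical Analysis section computes the primary outcomes as percentages, actual over target times 100, "to determine percent recruited, percent retained, and percent satisfied". It gives no target specific to satisfaction, no cut-off for counting as satisfied, and no rule on whose answer represents a dyad. On size it says: "A proposed sample size of 50 dyads, or parent-child pairs, will allow investigators to establish feasibility and proof of concept".

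Satisfaction is measured in one place, the paragraph that closes the Assessments section: "At the 6-month assessment only, all participants will complete an Exit Survey assessing" several topics, among them "perceived benefits and barriers to implementing intervention goals; overall satisfaction; and suggestions for improvement". The general schedule at the head of that section is "All assessments will occur at baseline, 3-, and 6-months (primary) unless otherwise noted", and the Exit Survey is a stated exception to it. The same closing paragraph adds: "Attendance and adherence will be monitored".

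The text describes no early-exit survey, no contact with families who withdraw or cannot be reached, and no rule for missing answers.

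**The concern.** The opening of the protocol gives feasibility, and support for a later application, as the study question. Families who leave are well placed to say what made the programme hard to continue. If the survey is given as timed, a family that has withdrawn or been lost by 6 months has no described occasion to answer. Part of a primary outcome is then unmeasured, and so is that family's account of barriers, for which the Exit Survey is also the only described source.

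Percent retained and attendance show how many families left and roughly when. They do not show whether those families were satisfied or why they stopped. Careful reporting afterwards can bound the missing answers but cannot recover them, so the route has to exist before families leave.

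**Working it through.** The plan gives no satisfaction figure to reproduce. The check is a reading of the text, followed by arithmetic on assumed rates.

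**Inputs from the documents.** 50 planned dyads (Recruitment; Statistical Analysis); percentage = actual/target × 100 (Statistical Analysis); Exit Survey at 6 months only (end of Assessments). Retention and satisfaction rates are not given, so every rate below is an assumption.

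**Undetermined part.** With N enrolled and S surveyed, the share of enrolled dyads whose satisfaction is unknown is (N − S)/N. With N = 50, each 5 dyads not surveyed give 5/50 = 10 points. This step needs no satisfaction rate. If enrolment differs from 50, N changes accordingly.

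**Example A: 40 surveyed, 36 satisfied.**
- Of respondents: 36/40 = 90%.
- Of enrolled, non-respondents counted as not satisfied: 36/50 = 72%.
- Of enrolled, non-respondents counted as satisfied: (36 + 10)/50 = 92%.
- Width: 20 points.

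**Example B: 30 surveyed, 27 satisfied.** Of respondents, 27/30 = 90% again. Of enrolled, 27/50 = 54% to (27 + 20)/50 = 94%, a width of 40 points. The respondent figure does not move while the unknown part doubles.

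**How the denominator matters (example A).** The all-enrolled value depends on how many of the 10 leavers were satisfied:

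| Leavers satisfied | All-enrolled value | Error of 90% (respondents) | Error of 72% (all dyads) |
|---|---|---|---|
| 0 | 36/50 = 72% | +18 | 0 |
| 5 | 41/50 = 82% | +8 | −10 |
| 9 | 45/50 = 90% | 0 | −18 |
| 10 | 46/50 = 92% | −2 | −20 |

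A respondent denominator overstates if leavers are less satisfied than respondents and understates if they are more satisfied. An all-dyad denominator treats every non-respondent as not satisfied, so it can only be right or too low.

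**What asking leavers would gain (example A).** If r of the 10 leavers reply, the width is (10 − r)/50:
- r = 0: 20 points
- r = 2: 16 points
- r = 6: 8 points
- r = 10: 0 points

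If 6 reply and 2 of them are satisfied, the enrolled figure runs from 38/50 = 76% to (38 + 4)/50 = 84%. The combined respondent figure is 38/46 = 83%, which conceals 90% at 6 months against 2/6 = 33% at early exit.

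**Exposure.** The Intervention section has a launch meeting in week 1, weekly sessions in weeks 2–12, then "bi-weekly 30-minute sessions with their coach weeks 13-24 (maintenance phase"), and "during the maintenance phase, dyads will select the topics of their choice for each session". Reading bi-weekly as every two weeks, that is 1 + 11 + 6 = 18 dyad sessions, not counting the orientation and the separate parent visits. A family leaving after week 12 has had at most 12 of the 18 and none of the self-chosen ones. This bears only on why early answers should be shown separately.

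**Respondent unit.** Suppose that among 40 surveyed dyads 36 parents and 32 children are satisfied. Requiring both gives 36 + 32 − 40 = 28 to 32 dyads (70% to 80% of 40). Accepting either gives 36 to 40 (90% to 100%).

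**The case against.** The strongest reply is that the plan says all participants complete the survey, not only attenders or completers. On this reading the word only merely excludes baseline and 3 months, and a family that stops coaching can still answer at 6 months. That stands. A reader might infer that everyone who stops the programme is excluded, but the text does not say so. The gap concerns families who withdraw from the study or are out of contact by 6 months. For them the plan may intend inclusion, but no described procedure delivers it.

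Second, a reader might infer that the plan will overstate satisfaction. The documents do not support that. The formula divides by a target, and if the target is all 50 dyads the plan would already report 72% in example A, so the 18-point excess would not arise. The direction stays open until the target is defined.

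Third, lost families may be the hardest to reach, and those who leave early rate a shorter programme. Both points stand. The gain depends on reply and may be nil, and early answers should not simply be pooled.

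Fourth, the survey instrument is not in the text, and the consent pages were removed from this copy. Either might say more, so the statement that no route is described is limited to the text available.

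Finally, rating the whole programme at its end is a defensible choice, and the study states no satisfaction threshold on which a decision turns. That limits the weight of the point. It does not remove it, since feasibility is what the study sets out to establish.

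**Conclusion.** The point holds as a low-cost improvement to a primary outcome; it does not invalidate the study. As described, the plan leaves satisfaction and barriers unmeasured in families who withdraw or are lost before 6 months. Given 50 enrolled, the unmeasured share is 10 points per 5 dyads not surveyed. The 72% to 92% range rests on the assumed 40 surveyed and 36 satisfied. The narrowing to 16, 8 or 0 points rests on 2, 6 or 10 of the 10 leavers replying, and with no replies nothing is gained. The undefined target, cut-off and respondent unit are missing detail. They matter here because they decide what the reported percentage means.

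**What to change.** In the Assessments section, replace the restriction to the 6-month assessment with wording such as: *The Exit Survey is offered electronically to each participant, parent and child, at withdrawal. At 6 months it is offered to all other enrolled participants whether or not they attend the assessment, including those out of contact, and again to those who did not answer at withdrawal. Each participant's survey is counted once.*

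In the Statistical Analysis section:
- Report percent satisfied over all enrolled dyads as the main figure, alongside the respondent figure, the number of non-respondents, and worst-case and best-case bounds (all non-respondents not satisfied; all satisfied).
- Show early-exit answers separately, because they rate a shorter exposure.
- Before data are seen, fix the target for this outcome, the cut-off for satisfied, and whether the parent's answer, the child's or both count for a dyad.

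The cost is one added survey trigger, one extra electronic contact with leaving families, and a few lines of analysis. The survey's mode is not stated, but REDCap already carries the psychosocial questionnaires. The downsides are incomplete reply from lost families and a possibly less favourable figure.

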Redesigning Pediatric Primary Care Obesity Treatment: Virtual House Calls

NCT06078774

09.19.2023

PROTOCOL

The Virtual HouseCalls model is designed to augment existing primary care approaches for management of childhood obesity preventing progression to severe obesity. This approach will leverage existing, widely accessible telehealth technologies to improve reach to populations with disparities in obesity prevalence. The goal is to develop an evidence-based intervention that could be widely integrated into pediatric patient-centered medical homes. The study question is to establish the feasibility of this intervention and support a future application.

STUDY AIMs:

Aim 1: To test the feasibility and preliminary efficacy of the Virtual HouseCalls intervention.

Aim 2: To test the preliminary efficacy of Virtual HouseCalls on BMI and secondary outcomes of parenting, child diet and physical activity, sleep and home food environment.

RECRUITMENT:

We plan to recruit 50 parent-child dyads using established strategies. Eligible families will be invited to an informed consent discussion virtually (Zoom) or in person, in which study procedures will be detailed, eligibility confirmed, and consent/assent obtained. Consented participants will receive detailed instructions for completing baseline assessments.

INTERVENTION:

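### The 6-month paired t-test leaves out every dyad lost after month 3, so the estimated change is biased if dropout depends on early response

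*Combined protocol and SAP*

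**What the plan says.** The ASSESSMENTS section sets three visits: "All assessments will occur at baseline, 3-, and 6-months (primary) unless otherwise noted". Under STATISTICAL ANALYSIS, the primary outcomes are percentages: "percent recruited, percent retained, and percent satisfied". Secondary outcomes get two treatments. The first is "descriptive statistics to calculate scale means and standard deviations at assessment time points". The second is the only test of change: "Paired samples t-tests will be used to examine changes in secondary outcomes over the course of the 6-month intervention".

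The second aim is "To test the preliminary efficacy of Virtual HouseCalls on BMI and secondary outcomes", and the opening paragraph says the study should "establish the feasibility of this intervention and support a future application". BMI is not among the primary percentages, so I take it to fall under the paired t-tests.

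Two further data streams exist: "Weight is assessed weekly by coaches" (INTERVENTION) and "Attendance and adherence will be monitored" (ASSESSMENTS). No analysis of either is described. The plan states no analysis set, missing-data rule, longitudinal model, expected retention rate or comparison of dropouts with completers.

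**The concern.** A paired test of 6-month minus baseline can use only dyads with both values. A family seen at baseline and month 3 but not at month 6 contributes nothing to the 6-month estimate. Its 3-month value appears only in a descriptive mean.

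That is harmless only if those who leave would have changed as much, on average, as those who stay. Families hear their child's weight result every week, so staying or leaving could plausibly depend on early response, though the documents do not show that it does. If families doing poorly leave more often, the completers look better than the enrolled group. If families doing well leave, the completers look worse. The plan contains no analysis that would show which applies.

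The 6-month change is the efficacy estimate likely to be carried into the future application. Retention is itself a primary outcome, so some loss is anticipated.

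**Working it through.** **Inputs from the documents.** 50 dyads; visits at 0, 3 and 6 months; paired t-tests. No dropout rate, SD, correlation, significance level or power is given, so there is no figure to reproduce. Everything below rests on assumed inputs. The unit is the SD of the 6-month change, and a negative sign means benefit, as for BMI.

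**Step 1: correlation between the 3- and 6-month changes.** With unit variance at each visit,

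ρ = (1 + r36 − r03 − r06) / √[(2 − 2·r03)(2 − 2·r06)].

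- Strong tracking, (r03, r06, r36) = (0.95, 0.90, 0.95): ρ = 0.10/√(0.10 × 0.20) = 0.707.
- Moderate tracking, (0.6, 0.5, 0.6): ρ = 0.50/√(0.80 × 1.00) = 0.559.

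**Step 2: large-sample bias of the completers' mean.** Let z be the standardised 3-month change and let P(dropout) = 1/(1 + exp[−(a + b·z)]), with a chosen to give the stated dropout. Then bias = ρ × E[z | retained]. Numerical integration gives:

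| Dropout | b | E[z given retained] | Bias, ρ = 0.559 | Bias, ρ = 0.707 |
|---|---|---|---|---|
| 10% | 0.7 | −0.067 | −0.037 | −0.047 |
| 10% | 1.0 | −0.091 | −0.051 | −0.064 |
| 20% | 0.7 | −0.130 | −0.073 | −0.092 |
| 20% | 1.0 | −0.173 | −0.097 | −0.122 |
| 30% | 0.7 | −0.192 | −0.107 | −0.135 |
| 30% | 1.0 | −0.253 | −0.141 | −0.179 |

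Reversing the sign of b (good responders leave) reverses the sign of the bias.

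**Step 3: simulation at n = 50.** There were 6,000 trials per scenario (3,000 at 10% dropout), with trivariate normal data, zero true change and |b| of 0.7-1.0 except in the unrelated-dropout row, where b = 0. False benefit is a significant result in the benefit direction from a two-sided 5% test, so nominally 2.5%. The model is maximum likelihood with unstructured covariance, a df-corrected standard error and completers − 3 df. Dropout is 20-30% unless stated.

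| Scenario | Paired bias | Paired false benefit | Model bias | Model false benefit |
|---|---|---|---|---|
| Poor responders leave after month 3 | −0.076 to −0.178 | 7.2-18.4% | at most 0.004 in size | 2.0-2.8% |
| Same, 10% dropout | −0.042 to −0.066 | 4.8-6.7% | not listed | not listed |
| Good responders leave | +0.073 to +0.180 | 0.1-0.8% | at most 0.004 in size | not listed |
| Dropout unrelated | at most 0.005 in size | not listed | at most 0.005 in size | not listed |
| Poor responders leave, half also lack month 3 | −0.072 to −0.180 | 6.9-18.3% | −0.019 to −0.070 | 3.4-6.3% |
| Dropout follows the unseen 6-month value | −0.129 to −0.254 | 12.8-34.2% | −0.066 to −0.160 | 6.0-17.6% |
| Outcome correlated only 0.3 with the dropout driver | −0.022 to −0.052 | 3.4-5.2% | at most 0.003 in size | not listed |

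The paired biases in the first three rows agree with Step 2. A repeat run of the first row gave 0.07-0.18 SD and 6-18%. A separate simulation of 20,000 trials per scenario with ρ = 0.7 agreed as well. At 20% dropout and an odds ratio of 2 per SD, completers' bias was −0.089 and two-sided rejection 8.9%. At 30% and an odds ratio of 3, it was −0.192 and 20.9%. The estimate using the 3-month changes was within 0.003 of zero throughout.

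**Step 4: scale.** With 80% power at two-sided 5% (noncentral t), the detectable change is 0.404 SD for 50 pairs, 0.454 for 40 (20% lost) and 0.487 for 35 (30% lost). The bias when poor responders leave is therefore 0.076/0.454 = 17% to 0.178/0.487 = 37% of a detectable effect.

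**Precision.** With informative dropout, the model's variance was between about the same and 10% lower. The argument rests on bias, not precision. Root mean squared error in the first scenario was 0.153-0.166 for the model against 0.176-0.241 for the paired test.

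**The case against.** - **Complete-case analysis is inferred.** The plan never uses the term, and its wording could also cover a baseline-to-3-month test. True, but a 3-month test would not repair the 6-month estimate, and no rule stated in the plan restores the missing dyads.
- **Leaving the programme is not the same as missing the 6-month visit.** The exit survey is meant for all participants, so families who stop sessions may still be measured. That is a fair point. If nearly everyone attends month 6, the problem largely disappears.
- **The direction could be worked out.** Three-month values, attendance and coach weights could show who left. Correct: the information will exist, and what is missing is a planned analysis of it.
- **The sizes are assumed.** At 10% dropout the bias is under half a standard error (1/√45 = 0.149 SD). Outcomes only loosely tied to what drives dropout are hardly affected. Both limits stand.
- **The remedy is partial.** It works best when loss comes after month 3 and depends on observed values. If dropout follows the unseen 6-month value, the model still gives 6-18% false benefit. This also stands, although its bias was smaller than the paired test's in every informative-dropout scenario where both are listed.
- **The exact recommended method was not simulated.** The simulation used maximum likelihood on normal data, not REML with Kenward-Roger degrees of freedom, and not short scales. The error rates are therefore indicative.
- **This is a feasibility study, and no control group is described.** Neither analysis makes the change attributable to the programme. That limits the consequence, but it does not justify adding an avoidable selection bias to a stated efficacy aim.

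**Conclusion.** The concern holds. As written, the 6-month test omits any dyad without a 6-month value and does not use the 3-month value already collected. Whether that biases the result depends on why families leave, which the documents do not say.

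The sizes in the working require 20-30% loss after month 3, a fairly strong link between early response and dropout (odds ratio about 2.0-2.7 per SD), and changes that correlate 0.56-0.71 between months 3 and 6. With high retention, unrelated dropout or a weak link, the effect is small or nil. The point touches the preliminary-efficacy aims only. It merits a change because the better analysis uses data already planned, not because the study fails without it.

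**What to change.** For each secondary outcome measured at all three visits:

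1. Make the main analysis a linear mixed model on all available data, with visit as a categorical fixed effect, unstructured within-person covariance, REML and Kenward-Roger degrees of freedom. Report the 0-to-6-month change with a 95% CI, and the 0-to-3-month change as supportive.
2. Keep the completers' paired t-test as a sensitivity analysis, and state the number of pairs.
3. Tabulate dropouts against completers on baseline values, 3-month values, attendance and last coach-recorded weight. Attendance and coach weights also describe dyads lost before month 3, whom the model helps little.
4. Add a missing-not-at-random check that sets the dropouts' 6-month mean 0.25 and 0.5 SD worse than the model predicts. With 20-30% missing, the estimate moves by 0.20 × 0.25 = 0.05 SD to 0.30 × 0.5 = 0.15 SD.

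The cost is a few lines of analysis plan, standard software and slightly more analysis work, with no new visits or measures. The model relies on data being missing at random. That is weaker than what the paired test needs, but it cannot be tested, hence item 4.
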